9.3 Variables

The investigator collects historic data (demographic and clinical characteristics) from medical records if available, or else by interviewing the patient. Likewise, the investigator collects treatment related data during initial visit and follow-up visits. The investigator documents the study-relevant data for each patient in the case report form (CRF). The CRF is available upon request. The respective document, <3>, is listed in Annex 1.

Table 2: Tabulated overview on variables collected during the study*

Variables	Initial visit	Follow-up visit(s)	Final visit
Demographics	X	X	X
Medical history	X		
Concomitant disease	X	X	X
Adverse Events**	X	X	X
PH etiology	X		
Pregnancy	X	X	X
Smoking history/status	X	X	X
Systemic BP before start of Adempas®	Х		
6 Minute Walking Test	X	X	X
NYHA/ WHO FC	X	X	X
Borg Dyspnoea Index	X	X	X
EQ5D VAS	X	X	X
Hemodynamic measurements, lung function, cardiac rhythm	X	X	X
Biomarkers	X	X	X
Laboratory tests	X	X	X
Treatment and concomitant medication	X	X	X
Resource use in hospital and outpatient care	X	X	X

^{*} Data are only collected on assessments that are performed routinely.

9.3.1 Variables to determine the primary endpoint(s)

The variables for primary objective are:

- Adverse events (AE) and serious adverse events (SAE)
- All-cause mortality

^{**}Serious Adverse Events must be reported to the sponsor within 24 hours.

9.3.2 Variables to determine the secondary endpoint(s)

The outcome variable(s) for secondary objective(s) is/are:

- AE and SAE in the different PH indications (PAH, CTEPH)
- Adverse events of interest
 - o Symptomatic Hypotension (date BP measurement, symptoms)
 - Haemoptysis and pulmonary haemorrhage (serious and non-serious). Specific information regarding relevant history, current condition, diagnostics, treatment, specific lab values and outcome to be documented in a specific CRF section in case AE/SAE of interest occurred
- Measurements of clinical effect
 - o 6 Minutes Walking Test,
 - o NYHA/ WHO FC
 - o Borg Dyspnoea Index
 - o EQ5D VAS
 - o Haemodynamic parameters from right heart catheter measurement
 - Biomarkers
- Resource use
 - O Hospitalization (due to PH or other reason, emergency admission, intensive care unit, number of days)
 - o Outpatient visits at PH center
 - Home care (nurse, days per week, hours per day), Rehabilitation/ nursery home (days)
 - Drug use, including switch or interruption or discontinuation of Adempas[®]
 and associated reason

9.3.3 Demographics

For demographic / socio-demographic assessment, the following data will be recorded:

- Year of birth
- Sex
- Height, Weight, BMI

9.3.4 Co-morbidities (medical history, concomitant diseases)

Co-morbidities are any medical findings, whether or not they pertain to the study indication, that were present before start of therapy with Adempas[®], independent on whether or not they are still present.

Findings meeting the criteria listed below are considered to be relevant to the study indication and have to be documented:

- Date of first PH diagnosis (month / year)
- Etiology of PH according to Dana Point Classification 2008, subgroups of CTEPH (inoperable, post-surgery), subgroups of PAH (monotherapy, combination therapy)
- Relevant concomitant diseases (e.g. vascular disease, diabetes, cancer)
- History of hemoptysis (date frequency, severity, bronchial arterial embolization (BAE), other pulmonary disease, trauma)
- Hepatic impairment (no/yes)
 - o Child-Pugh Classification
- Renal impairment (no/yes)
 - o Severity
 - o Estimated Glomerular Filtration Rate by Cockroft Gault formula

For any co-morbidity, the diagnosis, the start and the stop date/ongoing have to be documented.

9.3.5 Pregnancy

• Pregnancy Monitoring Form

9.3.6 Smoking

- Smoking history
- Current status

9.3.7 6-Minute Walking Test

- Date
- Distance

9.3.8 Functional class (WHO, NYHA)

- Date
- Result

9.3.9 Borg dyspnoea index

- Date
- Result

9.3.10 EQ5D visual analog scale,

- Date
- Score

9.3.11 Haemodynamic measurements

Date

- Mean pulmonary arterial pressure (mPAP, mmHg)
- Pulmonary vascular resistance (dyn*sec*cm-5)
- Pulmonary capillary wedge pressure (PCWP, mmHg)
- Right Atrial Pressure (RAP, mmHg)
- Cardiac index (L/min/m2)

9.3.12 Cardiac Rhythm

- Date
- Normal sinus rhythm, atrial fibrillation, atrial flutter or other arrhythmia

9.3.13 Lung function

- Date
- TLC, FVC, FEV1, DLCO, paO2, paCO2, O2 BGA

9.3.14 Biomarkers

- Brain Natriuretic Peptide (BNP; pg/mg or pmol/l)
- NT-pro BNP (pg/mg or pmol/l)

9.3.15 Laboratory tests

- Hemoglobin
- Hematocrit
- INR (if on VKA treatment)
- Creatinine
- Transaminases (ALT/AST)

Additional laboratory tests for CHD patients only

- Uric acid
- Sodium
- Iron, Ferritin, Transferrin, Soluble Transferrin Receptor, sTfR-Ferritin-Index
- C-reactive proteine
- MCV, MCH, MCHC
- Homocysteine

9.3.16 Prior and concomitant medication

All medication taken before study start (initiated and stopped before study start) is termed prior medication. All medication taken in addition (either initiated before study start or during the study) is termed concomitant medication.

Prior and concomitant medication meeting the criteria listed below are considered to be relevant and have to be documented:

- PH/PAH-specific therapy
 - o Adempas®
 - o ERA: bosentan, sitaxsentan, ambrisentan, macitentan
 - o PDE-5 inhibitors: sildenafil or tadalafil (physician will be alerted that the combination of PDE5 inhibitors with Adempas® is contraindicated)
 - prostacyclins
 - epoprostenol (Flolan)
 - treprostinil
 - iloprost
 - beraprost
 - o tyrosine kinase inhibitor: imatinib
 - o other specific targeted therapy: calcium channel blocker, other
 - o oral anticoagulation
 - Vitamin K antagonists
 - other
- other medications (only CHD: other cardiovascular drugs, antiplatelets)

Information to be documented includes:

- Trade name and INN
- Start and stop date
- Date of, dose, date of switch or addition of a specific drug/ Adempas®
- Reason for change (lack of efficacy or tolerability, patient's request, administrative)
- Dose
- Unit
- Frequency
- Administration mode
- Indication

Additional information on Adempas® to be documented includes:

- Individual dose after initial dose adjustment period
- BP before the 1st administration

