9.1.3 Strengths of study design

In this rare disease area a multinational exposure registry provides the ideal setting to monitor long-term drug safety and clinical effect in real clinical practice. This setting with a larger patient number than in regulated controlled clinical studies allows for a structured prospective documentation of long-term data on safety, clinical effect, and information on how Adempas® is used by PH experts. As Adempas® is the first sGC-stimulator in clinical use and all available clinical data derive from well-defined clinical studies, this registry may collect additional data on important potential safety risks, drug interactions and missing information.

The link with an existing, large and well established pulmonary hypertension registry is expected to enhance acceptance and facilitate patient recruitment for the study.

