9.7.4 Analysis of secondary outcome(s)

The secondary safety outcomes will be analyzed similar to the primary outcomes. Subgroup analyses will be conducted for selected secondary endpoints (e.g. 6 Minutes Walking Test, NYHA/WHO FC, hospitalization).

Analyses of adverse events will be conducted for PH subgroups (inoperable vs. post- surgery CTEPH patients, monotherapy vs. combination therapy PAH patients) .

Adverse events of interest will be analysed in detail. Adverse events of interest are

- Symptomatic hypotension
- Hemoptysis/ pulmonary haemorrhage

Further analyses of information on adverse events of interest as given by the detailed questionnaire and the AE page will be evaluated.

Kaplan Meier plots will describe the time until the individual events of interests

For the effectiveness variables summary statistics and changes form baseline will be calculated for

- 6 Minutes Walking Test,
- Borg Dyspnoea Index
- EO5D VAS
- Hemodynamic measurements
- Biomarkers

NYHA/WHO FC will be analyzed by frequency tables including changes from baseline.

The variables of hospitalization due to PH and drug utilization (reason and drug switch or interruption or discontinuation of Adempas®) will be analyzed by frequency tables and summary statistics.

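### Antiplatelets and other non-PH cardiovascular drugs must be documented only in CHD patients, so the events of interest cannot be described by these two drug classes in the full cohort

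*Protocol*

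**What the plan says.** Section 9.3.16 sets the scope of medication data: "Prior and concomitant medication meeting the criteria listed below are considered to be relevant and have to be documented". The list that follows has two parts.

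- **Without a CHD limit:** Adempas, ERAs, "PDE-5 inhibitors: sildenafil or tadalafil", prostacyclins, a tyrosine kinase inhibitor, "other specific targeted therapy: calcium channel blocker, other" and "oral anticoagulation" (vitamin K antagonists and other).
- **With a CHD limit:** "other medications (only CHD: other cardiovascular drugs, antiplatelets".

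For listed drugs, section 9.3.16 asks for start and stop date, dose and indication, among other items. Section 9.3.15 adds "INR (if on VKA treatment" among the laboratory tests for all patients.

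The events of interest (9.3.2, 9.7.4) are symptomatic hypotension and haemoptysis/pulmonary haemorrhage. Section 9.7.4 states: "Adverse events of interest will be analysed in detail". Section 9.7.3 plans incidence proportions and person-time rates, including those of the events of interest, stratified among other factors by concomitant medication use, and refers back to 9.3.16 for the categories. Section 9.1.3 gives as a strength of the design that "this registry may collect additional data on important potential safety risks, drug interactions and missing information".

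**The concern.** The data rule and the analysis aims do not fit together. The protocol singles out a hypotensive and a bleeding event for detailed analysis, stratifies safety by co-medication and mentions drug interactions. Yet it requires antiplatelets and non-PH cardiovascular drugs to be recorded only in one subgroup.

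A stratified incidence needs the exposure in patients with and without the event. If a class is not collected outside CHD, the SAP cannot create it as a full-cohort stratum. At stake is whether the registry can say how often these events occur in patients who do and do not take these drugs alongside Adempas.

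The subgroup is also unclear. CHD is in neither the abbreviation list nor the text as a defined term. The abbreviation is commonly used for both congenital and coronary heart disease, so sites could apply the limit differently.

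**Working it through.** The protocol states no figure for this point, so the main check sets its sections side by side.

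**1. What the planned analysis needs.** Section 9.7.3 defines two measures. For a co-medication stratum k they are:

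- incidence proportion = patients with the event in k / treated patients in k
- incidence rate = patients with the event in k / person-years on treatment in k

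Both need k to be known for every treated patient. If use changes over time, assigning person-years to k also needs start and stop dates.

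**2. What is collected, by class.**

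| Class | Required in all patients (9.3.16) | Named stratum (9.7.3) |
|---|---|---|
| Oral anticoagulation | yes | yes |
| PDE-5 inhibitors | yes | yes |
| ERAs | yes | yes |
| Prostacyclins | yes | yes |
| Calcium channel blockers | yes, under PH-specific targeted therapy | not named |
| Antiplatelets | CHD only | not named |
| Other cardiovascular drugs | CHD only | not named |

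Baseline systolic blood pressure is a further stratum in 9.7.3.

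**3. Whether another section closes the gap.**

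- *Event-triggered CRF section (9.3.2).* It asks for history, current condition, diagnostics, treatment, laboratory values and outcome once an event of interest has occurred. At best this gives the numerator in step 1. Patients without an event contribute nothing, so the denominator stays unknown.
- *Concomitant diseases (9.3.4).* Vascular disease is recorded in all patients, but the drugs given for it are not.
- *Causality assessment (11.1).* The investigator considers the patient's other drugs when judging an individual event. This again concerns cases only.
- *Table 2 (9.3).* Treatment and concomitant medication are documented at initial, follow-up and final visits, but what counts as relevant is set by 9.3.16.

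No section extends the two restricted classes to other patients.

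**4. Size of the group left out.** The protocol gives no CHD share s, so s is assumed. Of 900 planned patients (9.5), documentation is required in 900 × s and not required in 900 × (1 − s):

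- s = 5%: 45 required, 855 not
- s = 10%: 90 required, 810 not
- s = 20%: 180 required, 720 not

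**5. The protocol's one design figure.** Section 9.5 states an 83% probability of seeing at least three cases of an event with 0.5% incidence in 900 patients. The exact binomial value, 1 − P(X ≤ 2) with n = 900 and p = 0.005, is 0.827, so the figure reproduces. The point here does not depend on it.

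**The case against.** Several arguments on the other side carry weight.

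- **Important co-medications are covered.** A reader might infer that the events of interest cannot be stratified by the drugs most likely to confound them. The documents do not support that. Anticoagulants, plainly relevant to bleeding, and PDE-5 inhibitors and prostacyclins, relevant to blood pressure, are recorded in all patients and named as strata. Nothing in the protocol ranks antiplatelets or other cardiovascular drugs above them. This stands and narrows the point to two classes.
- **The study is descriptive.** It is uncontrolled and hypothesis-generating (9.1, 9.7.1), and the ENCePP checklist answers no on adjustment for confounding. A reader might infer a biased treatment effect, but no treatment comparison is planned. A confounding ratio would rest entirely on assumed prevalences and rate ratios. This stands too.
- **Drug interactions are not an objective.** Section 9.1.3 says only that such data may be collected, and sections 8.1 and 8.2 do not mention them. No named stratum fails for lack of these fields. This is fair, but 9.7.4 still promises detailed analysis of the events of interest.
- **Sites may record more, and records are kept.** The list is a minimum. Investigators keep a patient list for queries (10.5), and 15-year site retention is recommended (9.7.9). It would therefore go too far to call the data unrecoverable. But voluntary recording may be selective, and later retrieval means chart review in around 35 countries.
- **Strata may be thin.** At 0.5% incidence, 900 × 0.005 = 4.5 patients with the event are expected in the whole cohort, so a split by drug class would say little for events that rare. The protocol gives no expected incidence for the events of interest.

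**Conclusion.** The point holds in a limited form. Outside an undefined CHD group, antiplatelets and non-PH cardiovascular drugs need not be documented. The two events of interest therefore cannot be described by these classes in the full cohort. The loss is one of description: it limits the detailed analysis in 9.7.4, the concomitant-medication strata in 9.7.3 and the interaction data mentioned in 9.1.3. It does not invalidate the primary incidences or the strata already named.

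How many patients are affected depends on the CHD share, which is not given. On the assumed range of 5% to 20%, it is 720 to 855 of 900. The conclusion also assumes that sites record what is required and not systematically more. It is a cheap improvement to data collection, best made before the CRF is fixed.

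**What to change.** In 9.3.16, remove the CHD limit for antiplatelets and other cardiovascular drugs. Alternatively, record each class as yes/no with start and stop dates for all patients at initial, follow-up and final visits. Add both classes to the concomitant-medication strata in 9.7.3 for the events of interest. Define CHD in the abbreviation list, since it also governs the additional laboratory tests in 9.3.15.

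The cost is a small amount of extra data entry per patient. The items are already listed for CHD patients, medication is already documented at every visit type (Table 2), and the data come from routine records (9.4), so the non-interventional design is unaffected. Annex 1 lists the CRF as a draft still to be made available, so the change is easiest now. The strata can be detailed in the SAP, but the collection rule has to change in the protocol and CRF.

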9.4 Data sources

The investigator collects current and anamnestic patient data (demographic and clinical characteristics) from medical records if available. Likewise, the investigator collects treatment related data during visits that take place in routine practice. Each patient is identified by a unique central patient identification code, which is only used for study purposes. For the duration of the study and

afterwards, only the patient's investigator is able to identify the patient based on the patient identification code.

9.5 Study Size

It is planned to enrol 900 patients in specialized centers with the expectation to include a significant proportion of patients newly starting Adempas® monotherapy. This sample size allows detecting at least three "uncommon" AEs (with a probability of 83%) with an incidence of 0.5% (5/1000) or more. This is in the range of "uncommon" AE (0.1%=1/1000 to 1%=1/100). If the sample size increases to 1130, at least three "uncommon" AEs with incidence of 0.4% or more can be detected with the same probability.

9.6 Data management

A Contract Research Organization (CRO) will be selected and assigned for EDC system development. The CRF will be part of the EDC system which allows documentation of all outcome variables and covariates by all participating sites in a standardized way. Information on the EDC system is available upon request. The respective document, < 4>, is listed in Annex 1. Detailed information on data management, including procedures for data collection, retrieval and preparation are given in the Data Management Plan (DMP), which is available upon request. The respective document, <6>, is listed in Annex 1.

For information on quality control, refer to section 9.7.8.

9.7 Data analysis

9.7.1 Statistical considerations

Statistical analyses of this study will be of non-confirmative nature. This study is designed to support hypothesis generation.

All background variables and outcome parameters will be analyzed descriptively with appropriate statistical methods: categorical variables by frequency tables (absolute and relative frequencies) and continuous variables by summary statistics (i.e. mean, standard deviation, minimum, median, quartiles and maximum). Continuous variables will be described by absolute value and as change from baseline per analysis time point, if applicable.

All analyses will be performed for the total study population (overall analysis) and separately for PH subtype and subgroup, incident and prevalent patients, functional class at baseline, countries or regions if applicable and if patient numbers are sufficient. Prevalent patients is here defined as patients already on treatment, e.g. previously documented in the registry, whereas incident patients will be patients newly starting Adempas[®].

Patients receiving at least one dose of Adempas[®] will be included in the analysis. Whenever reasonable, data will be stratified by subgroups (e.g. age, gender).

All therapies documented will be coded using the World Health Organization – Drug Dictionary (WHO-DD). Medical history, any diseases and AEs will be coded using the latest Medical Dictionary for Regulatory Activities (MedDRA) version.

All statistical details including calculated variables and proposed format and content of tables will be detailed in the Statistical Analysis Plan (SAP). The SAP will be finalized before study database lock. The SAP is available upon request. The respective document, <7>, is listed in Annex 1.

It is planned to have at least yearly interim analysis/analyses e.g. for the purpose of the PSUR. The proportion of incident and prevalent subjects will be tracked. Analyses will refer to the primary and secondary objective. The final analysis will be performed after end of the study which is the date the analytical dataset is completely available.

All background data such as patient demographics, PH group and indication-specific characteristics and prior or concomitant medication of PH, and concomitant diseases will be described by presenting frequency distributions and/or basic summary statistics.

Sample size and disposition information by analysis time point will be displayed in a frequency table.

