Study size	It is planned to enroll 900 patients with the aim to include a significant proportion of patients newly starting Adempas® treatment. This sample size allows detecting at least three "uncommon" AEs (with a probability of 83%) with an incidence of 0.5% (5/1000) or more.		
Data analysis	All background variables and outcome parameters will be analyzed descriptively with appropriate statistical methods: categorical variables by frequency tables (absolute and relative frequencies) and continuous variables by summary statistics (i.e. mean, standard deviation, minimum, median, quartiles and maximum). Continuous variables will be described by absolute value and as change from baseline per analysis time point, if applicable.		
	All analyses will be performed for the total study population (overall analysis) and separately for PH subtype, patients who newly started or have already been on Adempas®, countries or regions if applicable and if patient numbers are sufficient, and in patients receiving at least one dose of Adempas®. All statistical details will be described in the Statistical Analysis Plan (SAP). It is planned to have yearly interim analyses on primary and secondary endpoints for the purpose of the PSUR and a final analysis after end of the study.		
Milestones	Start of data collection will be in April 2014 after official EMA approval with inclusion of the first patient (FPFV). With a recruitment period of 3 years and an observation period of 1-4 years LPLV is planned for April 2018.		

5 Amendments and updates

NA

6 Milestones

Definitions:

• Start of study: first center initiated

• Start of data collection: date of first data entry in database (prospective studies usually: FPFV;

retrospective studies: start of data entry)

• End of data collection: date of last data entry in database (usually after LPLV)

• End of study: database close

• Observation period: time-window for data collection (usually FPFV to LPLV)

• Final report: Final report of study results 12 months after database close

Table 1 presents planned milestones for the project. These milestones are based on a timely review and approval of the project. Administrative changes to milestones due to delays in study preparation and enrolment do not require amendments to the protocol.

Table 1: Milestones

Milestone	Planned date
Registration in the EU PAS register	Mar 2014
Start of data collection	Apr 2014
End of data collection	Apr 2018
Final report of study results	Aug 2018

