9.7.3 Analysis of primary outcome(s)

The main goal of this global registry is to assess the long-term safety of Adempas® in real life clinical use. Incidences of treatment-emergent adverse events, serious adverse events and all-cause mortality will be calculated, including adverse events of interest. An adverse event is considered as treatment-emergent when it has started or worsened after first application of study medication up to 2 days after end of treatment with study medication.

For the events the 'raw' incidence proportion (regardless of the time each patient is treated), i.e. number of patients with events divided by the number of treated patients, will be presented as well as incidence rates, i.e. number of patients with events divided by the cumulative person-time on treatment (person-years) separately for incident and prevalent patients.

The statistics will be calculated for Adempas[®] and stratified for medically relevant subgroups, e.g.

- Age
- Gender
- Etiology (Dana Point Classification of PH)
- · Hepatic impairment at baseline
- Renal impairment at baseline
- WHO functional class/NYHA group at baseline
- According to e.g. 6 MWD thresholds >= 380 m versus < 380m at baseline
- Type of PH pre-treatment
- Concomitant medication use
- Systolic blood pressure at baseline

The subgroup 'Type of PH pre-treatment' will include the categories 'therapy-naïve', 'pre-treated with ERA', 'pre-treated with PDE5 inhibitors', 'pre-treated with prostacyclins' and 'pre-treated with Adempas[®].

The 'Concomitant medication use' subgroup categories will refer to e.g. 'concomitant ERA', 'concomitant PDE 5 inhibitors', 'concomitant prostacyclins' and 'concomitant oral anticoagulation' see section 9.3.16 Details will be found in the SAP.

A comprehensive list of medically relevant subgroups will be added to the SAP.

Tables which show the incidence proportion of adverse events overall and by MedDRA preferred term within the primary SOC will also be presented. Incidences of adverse events and serious adverse events starting more than 2 days after end of treatment will be tabulated separately.

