Annex 1. List of stand-alone documents

Table 3: List of stand-alone documents

Number	Document name	Date	Title
1	AD1301_SC members	1/28/2014	List of Steering committee members
2	AD1301_countries	Will be available at end of recruitment	List of all countries
3	AD1301_INV_CRF	Will be available at time of first country ready to enroll	CRF draft
4	AD1301_EDC_summary	Will be available at time of first country ready to enroll	EDC System description
5	AD1301_EDC_validation	Will be available at time of first country ready to enroll	EDC System Validation
6	AD1301_DAT_DMP	Will be available at time of first country ready to enroll	Data Management Plan
7	AD1301_DAT_SAP	Will be available before study database lock	Statistical Analysis Plan
8	AD1301_DAT_QRP	Will be available at time of first country ready to enroll	Quality Review Plan

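### The SAP need be final only before database lock, after about three yearly interim analyses have shown outcomes, so the subgroup and cut-off details left to it could be set with results known

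*Protocol*

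**What the plan says.** Protocol section 9.7.1 sets the deadline: "The SAP will be finalized before study database lock". Annex 1 gives the same timing for the SAP (document 7): "Will be available before study database lock".

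On interim analyses, section 9.7.1 says "It is planned to have at least yearly interim analysis/analyses e.g. for the purpose of the PSUR" and adds "Analyses will refer to the primary and secondary objective". The Abstract (section 4) is more explicit: "It is planned to have yearly interim analyses on primary and secondary endpoints for the purpose of the PSUR".

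On the calendar, the Abstract says "Start of data collection will be in April 2014" and "With a recruitment period of 3 years and an observation period of 1-4 years LPLV is planned for April 2018". Table 1 in section 6 also ends data collection in April 2018.

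On what the SAP will settle, section 9.7.1 leaves statistical detail to it, including calculated variables. Section 9.7.3 adds: "A comprehensive list of medically relevant subgroups will be added to the SAP".

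**The concern.** Finalising a plan before lock is a real safeguard in a masked comparative trial, because results by arm are unknown until then. Here the design is a single uncontrolled cohort (section 9.1). There is nothing to unmask: a yearly table of adverse events, serious adverse events and deaths is the outcome. By the date the protocol sets for the SAP, such tables will have been produced several times.

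Two things are at stake. First, a reader of the final report could not tell which subgroups and cut-offs were chosen in advance and which were prompted by an interim result. Second, an interim report that shows subgroups or visit windows must use some definition of them. If no final document governs that definition, it may differ from one year to the next, and a change in a subgroup figure could then reflect the definition and not the drug.

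**Working it through.** The protocol gives no figure on this point to reproduce, and its sample-size calculation is not involved. The check is a calendar count, an estimate of how much information the interims would hold, and a comparison of what is fixed with what is open.

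**1. Interims before lock.** Inputs: start April 2014 and end of data collection April 2018 (Abstract; Table 1), with analyses at least yearly (9.7.1). Yearly points strictly before April 2018 are April 2015, April 2016 and April 2017, so 3. The protocol names no cut dates, so the April dates are inferred; at least yearly makes three a minimum on this calendar. Lock cannot precede the end of data collection, so it comes no earlier than about April 2018.

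**2. Information available at each interim.** Inputs: 900 patients (9.5), 3 years of recruitment and follow-up to year 4 (Abstract). Assumptions: uniform accrual of 900 / 3 = 300 patients a year, with no discontinuation.

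- Person-years by year t, for t up to 3: 300 × t² / 2 = 150 t².
- Total by year 4: mean entry time is 1.5 years, so 900 × (4 − 1.5) = 2250.
- Year 1: 150 / 2250 = 6.7%, with 300 patients enrolled.
- Year 2: 600 / 2250 = 26.7%, with 600 enrolled.
- Year 3: 1350 / 2250 = 60%, with all 900 enrolled.

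With constant discontinuation rates of 0.1, 0.2 and 0.3 a year, the year-3 share becomes 62%, 65% and 67%. So about 60 to 67% of person-time is seen by the third interim, and about 33 to 40% is still to come.

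**3. Fixed in the protocol already.**

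- Primary endpoints (9.1.1).
- Analysis population and the incident/prevalent distinction (9.7.1).
- Treatment-emergent window, to 2 days after end of treatment; numerators and denominators of the incidence proportion and incidence rate; tabulation by preferred term within system organ class; pre-treatment categories (9.7.3).
- Adverse events of interest and the CTEPH and PAH subgroups (9.7.4).

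**4. Left open until the SAP.**

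- The comprehensive subgroup list; the ten factors in 9.7.3 are given as examples.
- Cut-offs for age and systolic blood pressure, for which none is given, and for 6-minute walking distance, where 380 m is only an example.
- Concomitant-medication categories, also given as examples (9.7.3).
- Calculated variables (9.7.1).
- Analysis time windows: 9.7.2 refers to them without defining them, and 9.2.7 sets no exact follow-up dates. They affect dose by visit and every change from baseline.

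**5. The Annex 1 dates side by side.** The CRF, the EDC description, the EDC validation, the Data Management Plan and the Quality Review Plan are all due by the time a first country can enrol. The country list follows at the end of recruitment. The SAP alone is tied to database lock, and no section asks for a draft or earlier version before the first interim.

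**The case against.** The strongest reply is that this is a descriptive safety registry. Section 9.7.1 calls the analyses non-confirmative and hypothesis-generating, and no test, significance level or stopping rule is planned. The interims serve periodic safety reporting, and looking at a new subgroup after a signal is proper pharmacovigilance. The deadline is also a latest date: it does not forbid an earlier SAP. And leaving cut-offs and the full subgroup list to a SAP is normal practice.

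Most of this stands, and it limits the point. Leaving these items to the SAP is not at fault; the date by which they must be settled is. That the deadline permits earlier finalisation means the problem may not arise, but nothing in the protocol prevents it. Adding subgroups after a signal is legitimate provided the reader is told, and the protocol does not provide for that.

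Three stronger readings are tempting, and the documents do not support them:

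- A reader might infer inflated type I error and count chance-significant splits. No tests are planned, so that arithmetic does not apply. Most of the listed factors are also categorical; only age, systolic blood pressure and 6-minute walking distance clearly need a numerical cut-off.
- A reader might infer that the yearly safety results rest on undefined quantities. The overall primary rates do not: their formulas, window and population are in 9.7.1 and 9.7.3.
- A reader might infer that finalising before lock has no value here. On the assumptions above, a third or more of the person-time is still unobserved at the third interim.

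**Conclusion.** The point holds in a limited form. As written, the protocol allows the SAP to be completed after about three rounds of primary and secondary results have been seen in an uncontrolled cohort, with roughly 60 to 67% of person-time already observed. The count rests on the planned April 2014 to April 2018 calendar and one interim a year. The share rests on uniform accrual of 900 patients and the discontinuation rates shown.

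The exposure is confined to the open items listed in step 4 of the working. The consequence is possible data-driven subgroup reporting and weaker comparability between yearly reports. The overall incidence of adverse events, serious adverse events and death is not undermined. The importance is modest, but the change is worth making because it is specific and costs little.

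**What to change.** In section 9.7.1 and in the Annex 1 entry for document 7, replace the database-lock deadline with wording to this effect: SAP version 1 is final before the data cut for the first yearly interim analysis. It covers the subgroup list, the cut-offs for age, systolic blood pressure and 6-minute walking distance, the concomitant-medication categories, the calculated variables and the analysis time windows. Later changes or added subgroups are dated, justified and labelled as made after interim results.

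Run each interim report on the SAP version then in force and state that version in the report. New safety questions can still be pursued, provided they carry that label.

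The cost is writing the SAP earlier and keeping version control. Sites, data collection and sample size are unaffected.
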